Design: A sample of convenience will be used. Following consent and baseline data collection, participants will be assigned to one of two coaching methods, face to face format or phone. Participants who receive coaching over the phone will follow the exact procedures as face to face except coaching will be provided over the phone. The OPC intervention will last up to 10 weeks. Participants will be involved in the study for up to 18 months including baseline data collection, the intervention, and follow up data collection.

Sample: A convenience sample of up to 20 female primary caregivers, including but not limited to mothers, grandmothers and aunts of children with SCI will be recruited from three facilities specializing in pediatric SCI care and rehabilitation using the following inclusion and exclusion criteria:

Inclusion Criteria

1. Female primary caregivers of children with traumatic or acquired, non-progressive SCI between 6 and 13 years of age
2. Female primary caregivers will have legal guardianship of their child with SCI;
3. Speak, read and comprehend English
4. be available for face-to-face visits at a location in close proximity to the coach who will be providing coaching
5. have a cell phone with text messaging capabilities; be willing to utilize cell phone or land line for coaching
6. be able to verbalize challenges in their own participation or their child's participation during initial screening
7. Provide written consent

Exclusion Criteria

1. Severe mental health condition (female primary caregiver) as documented in the child's medical record or reported to research staff by child's treating physician or medical team member
 - a. If potential participants experience emotional distress, a qualified mental health professional will be available to provide appropriate resources or referrals if needed.
 - b. This would be documented in the child's medical record as standard procedure by the qualified mental health professional
2. Abuses or addictions (female primary caregiver) to illicit or prescribed substances or alcohol at the time of screening as documented in the child's medical record or reported to research staff by the child's treating physician or medical team member
3. Have a child with a diagnosis of suspected conversion syndrome at the time of screening as documented in the child's medical record or reported to research staff by the child's treating physician or medical team member

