4. Have a child who is suicidal at the time of screening as documented in the child's medical or reported to research staff by the child's treating physician or medical team member
 - a. If suicidal ideation (including intent and/or plan) is communicated at any point research staff will connect the participant with the qualified mental health professional who will conduct a suicide risk assessment and if needed, break confidentiality to call emergency personnel.
 - b. This would be documented in the child's medical record as standard procedure by the qualified mental health professional

Facilities: Three facilities specializing in pediatric SCI care and rehabilitation will recruit for and enroll participants in the study 1) Shriners Hospitals for Children- Chicago 2) Shriners Hospitals for Children – Philadelphia and 3) TIRR Memorial Hermann- Houston. Thomas Jefferson University is the regulatory and lead site, however no participants will be enrolled at this site. Each enrolling site will have 1-2 trained coaches who will each recruit, enroll, and complete the study procedures for data collection with up to 5 participants.

Data Collection and Study Procedures:

1. Following consent, screening, and enrollment, baseline data collection will occur including baseline demographics of caregiver and child characteristics, the Beck Anxiety Inventory, the International Spinal Cord Injury Basic Data Set for Primary Caregivers, and the International Spinal Cord Injury Pediatric Activities and Participation Basic Data Set.
2. Each coach will provide the intervention to up to 5 participants. Participants will be assigned to coaching method based on their order of enrollment. Depending on the coach, the first 1-2 participants enrolled will have face to face coaching. The next 1-3 participants will have phone coaching. Seven female primary caregivers will receive the face to face and 9 will receive the phone coaching, for a total of 16 participants to receive the intervention.
3. In the event that face to face is not feasible, participants will have coaching via phone.
4. Caregivers who are have face to face coaching will receive up to 10 coaching sessions at a location that is mutually convenient for the caregiver and coach.
 - a. The caregiver and coach will decide on how the sessions will be distributed over a 10 week period
 - b. All 10 sessions must be completed within a 10 week period
 - c. Each session will not exceed 90 minutes

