3. Fidelity: Descriptive and summary statistics will be used to identify the number (mean, mode and range) of coaching sessions conducted for the face-to-face OPC group and the phone OPC group, and the average number and range of sessions required for goal attainment. We will also identify the average time per OPC session for both groups. The number of missed sessions and reasons for missing sessions will be identified. We will examine variability among the four coaches, and will determine if significant differences in these variables exist between OPC face-to-face and phone OPC. These data will be used to define the dosing parameters of OPC for a future RCT.
4. The audio-recordings of each OPC session will be transcribed verbatim. The transcriptions will be read and evaluated on treatment fidelity. Inter-rater reliability on treatment fidelity between the two graduate assistants will be evaluated by calculating intraclass correlation coefficients (ICC, Model 2,1) with 95% confidence intervals (CI). The PI will randomly select 10 transcribed face-to-face OPC sessions and 10 phone OPC sessions, and will also assess

treatment fidelity. Agreement between the assessments of fidelity will serve as an internal quality control, but will also further assess reliability using ICC (2,1) with 95% CI.

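### The Fidelity analysis makes a significance comparison of 7 face-to-face with 9 phone caregivers one input to RCT dosing, with no interval for the difference, so a null result could be misread as equal need

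*Combined protocol and SAP*

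**What the plan says.** All references are to the combined protocol and SAP.

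- **Data Handling and Analysis, item 3 (Fidelity)** starts descriptively: "Descriptive and summary statistics will be used to identify the number (mean, mode and range) of coaching sessions conducted" in each format. It adds the sessions needed to reach goals, mean time per session, missed sessions with reasons, and the spread across the four coaches.
- The same item then says the study "will determine if significant differences in these variables exist between OPC face-to-face and phone OPC". It closes: "These data will be used to define the dosing parameters of OPC for a future RCT".
- **Data Collection and Study Procedures, item 2** gives the group sizes: "Seven female primary caregivers will receive the face to face and 9 will receive the phone coaching". The stated total is 16. The **Sample** paragraph allows "A convenience sample of up to 20 female primary caregivers", with no split by format for 20.
- **The same section, items 2 and 3,** sets the allocation: "Participants will be assigned to coaching method based on their order of enrollment", with face-to-face first within each coach, and "In the event that face to face is not feasible, participants will have coaching via phone".

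For the between-format comparison the plan names no test, significance level, sidedness, detectable difference, confidence interval or equivalence margin. It does not say whether the unit of analysis is the caregiver or the session. Item 4, by contrast, does plan 95% confidence intervals for its reliability coefficients.

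**The concern.** Objective 6 in Specific Aims makes the dosage and delivery of OPC for the RCT a product of this study. What the RCT designers need from item 3 is how many sessions, and of what length, each format takes, and how uncertain those figures are. A verdict of significant or not significant answers a different question. At 7 versus 9 the verdict will often be non-significant even when the formats differ materially.

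The summaries listed in item 3 (mean, mode, range, counts) do not show the precision of a between-format difference. The significance result is therefore the only planned inferential statement on whether the formats differ. With no interval beside it, a null result could be carried into the RCT as evidence that one dose suits both formats.

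**Working it through.** **The plan's own figure.** There is none to reproduce: no power, significance level or target difference is stated. The only internal check is 7 + 9 = 16, which agrees with the stated total.

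**Inputs**
- From the plan: n₁ = 7 face-to-face, n₂ = 9 phone, and at most 10 sessions per caregiver.
- Assumed, because the plan is silent: a two-sided 5% level; a true difference of 1 SD (0.5 to 2 SD shown); one independent, roughly normal value per caregiver; and, for scale only, an SD of 2 to 3 sessions.

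**Step 1. Standard error of the difference, in SD units**
√(1/7 + 1/9) = √0.2540 = 0.504.

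**Step 2. Power of the two-sample t test**
Degrees of freedom = 7 + 9 − 2 = 14, and the critical value is t(0.975, 14) = 2.145. At a difference of 1 SD the noncentrality is 1/0.504 = 1.98. The noncentral t distribution gives:

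| True difference | Power |
|---|---|
| 0.5 SD | 15% |
| 0.8 SD | 32% |
| 1.0 SD | 45.5% |
| 1.2 SD | 60% |
| 1.5 SD | 79% |
| 2.0 SD | 96% |

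Power reaches 50% at 1.06 SD and 80% at 1.52 SD. The Mann-Whitney test, simulated on normal data at 1 SD, gives about 40% (20,000 runs, exact p-values). For comparison, 80% power at 1 SD would take 17 caregivers per group by the t test.

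**Step 3. Width of the 95% interval**
Half-width = 2.145 × 0.504 = 1.08 SD. This is also the smallest observed difference that the t test can call significant, so an observed difference of 1 SD would be reported as non-significant.

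**Step 4. On the scale of sessions**
With an SD of 2, 1.08 × 2 = 2.2 sessions either way. With an SD of 3, 1.08 × 3 = 3.2 sessions either way. The maximum is 10.

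**Step 5. Sensitivity of the 1 SD result**

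| Setting | Power at 1 SD |
|---|---|
| 7 v 9, one-sided 5% or two-sided 10% | 60% |
| 10 v 10, two-sided 5% (if all 20 were coached and split evenly) | 56% |
| 7 v 9, normal approximation (optimistic at this size) | 51% |
| 5 v 11, two-sided 5% (if two caregivers move to phone) | 41% |

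Even at 56% to 60% power, a 1 SD difference is missed 40% to 44% of the time.

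**Step 6. What the arithmetic leaves out**
- Caregivers are grouped by coach, and format follows enrolment order within coach. The calculation ignores both.
- Sessions to goal attainment exist only for caregivers who attain their goals, so that comparison may have fewer than 7 and 9.
- If sessions were analysed as independent, up to 7 × 10 = 70 and 9 × 10 = 90 records would stand in for 7 and 9 people, and the interval for time per session would probably be too narrow.

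**The case against.** The strongest reply is that item 3 is mainly descriptive. The sentence on dosing refers to the data of the whole item, and the significance comparison is half of one sentence. Session counts and session time by format are already planned, so much of what the RCT needs will be there. The item sits under the secondary exploratory heading of a feasibility study, where low power is expected and sample size estimation is an output. All of this stands and limits the point to a small one. It does not supply the missing precision: a small exploratory study is a reason to estimate rather than to test.

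Three stronger readings are tempting, and the documents do not support them.

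- A reader might infer that the RCT dosing depends on the tests alone. It does not; the descriptive summaries feed it too.
- A reader might infer that non-significance will be taken as equal dosing. No such rule is written, and nothing says that a common dose would follow. The most that can be said is that the plan leaves room for that misreading.
- A reader might add a familywise error figure for several unadjusted tests. The usual formula needs independent tests. Here, coaching stops once goals are met, so sessions held and sessions to goal attainment overlap by design. The comparisons are also labelled exploratory.

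It is also fair to say that a confidence interval does not cure non-random allocation. An interval that ignores enrolment order and coach still describes a contrast in which format is mixed with both, so the fix has to say so.

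**Conclusion.** The point holds as a minor one. Item 3 uses an unspecified significance comparison of 7 with 9 caregivers as one input to RCT dosing and plans no interval for the difference. At an assumed two-sided 5% level and a true difference of 1 SD, power is about 40% (Mann-Whitney) to 46% (t test), and the 95% half-width is about 1.08 SD.

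That the test misses a 1 SD difference more often than not depends on those assumptions and is close to the line; Step 5 shows settings in which it fails. The conclusion does not turn on which side of 50% the power falls. In every setting shown, a non-significant result is weak evidence that the formats need the same number or length of sessions. The fault lies in the form of the comparison, not in the size of a feasibility sample.

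**What to change.** In item 3, replace "will determine if significant differences in these variables exist between OPC face-to-face and phone OPC" with wording such as:

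> *will estimate the face-to-face minus phone difference, with its 95% confidence interval, for each variable, using one value per caregiver. These comparisons are exploratory; non-significance, or an interval that includes zero, will not be taken as equality. Because format is assigned by enrolment order within coach, differences will not be attributed to format alone.*

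Base the RCT dosing parameters on each format's own estimate and interval. State the interval method in advance, since session counts are capped at 10 and the groups are small, and give the number of caregivers behind each estimate.

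The cost is a few lines of analysis text, with no new data, participants or visits. The sponsor gives up p-values that carry little information at this size.
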